## **Thirty Million Words Initiative Newborn Implementation Trial**

### **Protocol Narrative**

The Thirty Million Words Initiative Newborn Intervention (TMW-Newborn) is a public health effort aimed at increasing awareness about the importance of a child's early language environment in his or her first years of life. This one-time educational intervention will be impacting maternal awareness and knowledge about the importance of children's early language environment, between ages 0 and 3. We envision the intervention to be carried out in the immediate postpartum period because we seek to provide language enriching tools parents can use with their babies from the start. The educational intervention will be delivered in conjunction with the Universal Newborn Hearing Screening (UNHS) in partnering hospitals, an existing public health infrastructure and a routine part of postpartum care.

#### **Background**

The Newborn Initiative is both an extension and a focused adaptation of the larger Thirty Million Words initiative. TMW-Newborn is grounded in three main bodies of literature and avenues of research. The first is research on early childhood language acquisition, child development, and child behavior. The foundation of our evidence-based research derives from the differences found in children's language environments, which largely depend on socio-economic status (Hart and Risley 1995). Second is research on maternal health education and health literacy, specifically on prenatal, perinatal and post-natal education. Third is research and data on the Universal Newborn Hearing Screening (UNHS), which occurs during post-partum care. The UNHS is a critical point in time to both deliver the TMW message and to increase follow up for those newborns not passing the initial screening by focusing on the importance of a child's early language environment and the impact of hearing loss on cognitive development.

Our effort therefore lies in bringing these three main bodies of research together to craft a public health intervention, which relies on existing initiatives while adding an important educational component. TMW-Newborn not only aims to impact parents' beliefs about how crucial their role is in creating a stimulating and enriching language environment for their baby, but also seeks to improve rates of re-screening (loss to follow-up) for the universal newborn hearing screening. By emphasizing the importance of talk (and hearing) for cognitive and language development, we seek to encourage families to follow up after the screening if their newborn does not pass.

#### ***Importance of Language Acquisition on Cognitive Development:***

A child's early language exposure is increasingly acknowledged as pivotal in language development and, more importantly, in ultimate educational and intellectual achievement (Bruner, 1981; Chapman, 2000; Gallaway & Richards, 1994; Hart & Risley, 1995; Huttenlocher, Haight, Bryk, Selzer, & Lyons, 1991; Rowe, 2008). Hart and Risley's landmark study demonstrated the tremendous impact of a child's early language milieu on future learning, revealing a significant correlation between the number of words a child is exposed to between ages 0-3 and his/her ultimate IQ and academic success (Hart & Risley, 1992; 1995). Their

findings were both significant and alarming, demonstrating the critical and time-sensitive role that early language exposure plays in a child's life.

The tragedy for children born into poverty is the overwhelming inequity in their early language experience. Hart and Risley's study revealed a steep socioeconomic gradient in early exposure to words/language. At the end of their third year, children from high socioeconomic status (SES) families heard approximately *forty-five million* words; children from economically impoverished backgrounds heard only approximately *thirteen million*. Hart and Risley found that "with few exceptions, the more parents talked to their children, the faster children's vocabularies were growing and the higher their children's IQ test scores at age three and later." Their follow-up with these children at 9-10 years of age confirmed that preschool/school interventions came too late to alter these trajectories; the reverberations of early linguistic shortfall were likely to follow these children throughout their lives.

But the tragedy for these children is not unalterable. It is neither genetics nor a lack of potential that lies at the heart of this inequity; it is parental knowledge. In 2008, Rowe demonstrated that the relationship between socioeconomic status and parental communication ability is mediated by parental knowledge (Rowe 2008). Other studies have corroborated this, showing that the effect of socioeconomic status on a child's vocabulary was primarily dictated by maternal speech (Hoff 2003). Encouragingly, studies have also demonstrated that a well-planned, parent-directed language intervention in low-income populations may have a positive effect with parents increasing their use of facilitative language with their children (Oneil-Pirozzi, 2009).

***Universal Newborn Hearing Screening and Early Hearing Detection and Intervention:***

Since 2000, the number of infants screened for hearing loss at birth has dramatically increased. According to 2011 data (Centers for Disease Control and Prevention, 2013), 97.9 % of all babies in the United States receive the Universal Newborn Hearing Screening. However, 1.8 % of newborns (59,161) do not pass the screening, 35.3% (20,857) of which are not rescreened, failing to receive the next step of treatment. The CDC groups these failed re-screenings into two categories: "Loss to Follow-Up (LFU)" and "Loss to Documentation (LTD)". For infants who did not pass the newborn hearing screening, LFU refers to a failure to receive the next step of treatment, be it rescreening or comprehensive audiologic evaluation. Families are contacted but do not follow up, or cannot be contacted. LTD refers to failure to report the results from hearing screening, rescreening, diagnostic services, and/or treatment services which are needed for comprehensive surveillance and monitoring by Early Hearing Detection and Intervention (EDHI) and the medical home.

In Illinois, all birthing hospitals perform the newborn hearing screening, and 99.4% (156,376 in 2011) of newborns are screened for hearing loss (Centers for Disease Control and Prevention, 2013). According to 2011 data however, of the 2,714 infants not passing the test, 64% (1,736) are LFU or LTD. This is nearly double the national average. The high incidence of newborns not returning for a complete audiologic screening is worrying and constitutes a concern for newborn developmental health. An infant who does not pass his/her newborn hearing

screening has a potential developmental emergency because of the tremendous impact language has on the developing brain.

***A Participatory Model of Educational Intervention:***

The educational intervention is currently being designed and planned with iterative participation and feedback from the audience we seek to have an impact on. Exploratory and formative qualitative research informs the intervention, drawing insights from pregnant mothers, mothers in immediate post-partum, parents, and healthcare providers. Our intervention is currently being developed with focus groups and individual interviews with mothers and parents, consultation with medical professionals (RNs, OB GYNs, Pediatricians), and visits to community health centers and birthing hospitals in Pensacola, FL to understand the feasibility of implementation of the intervention around the time of the newborn hearing screening.

The TMW-Newborn translates the TMW message into a shorter-format one-time educational intervention that can be delivered to new parents in the hospital as part of routine postpartum care. As a large-scale public health approach, it has the potential for a significant impact on SES-disparities in language development. While the earlier TMW intervention was developed for toddlers, the TMW-Newborn intervention will be tailored for parents of newborns. It will include messages and strategies specifically for children from birth to one year of age with a focus on preverbal communication and mother-child attachment. It will also include video modeling of parents utilizing both spoken and sign language. Given the novelty of this intervention, it will be important to evaluate its acceptability and feasibility with low-SES families and objectively examine evidence of its efficacy. The TMW NI video will be available in both English and Spanish.

***The significance of the Newborn Intervention as a Public Health Initiative***

The Thirty Million Words Initiative Newborn Intervention is a public health effort to raise awareness about the critical importance of early childhood language development. It will occur at the beginning of a baby's life and during a special time for his or her parents, right after delivery. TMW-Newborn is situated at the intersection of multiple public health initiatives: the Universal Newborn Hearing Screening and Early Hearing Detection and Intervention are crucial public health interventions to timely screen and detect hearing loss. For the intervention, TMW-Newborn will be integrated as part of routine postpartum care in the hospital stay. In the future, we envision having key information about child language development as part of the discharge packet every mother receives after birth. We also seek to have key information of language development milestones in newborns be part of prenatal classes and be included in prenatal educational material.

***Previous Research***

We conducted two randomized controlled trials to evaluate the feasibility and efficacy of TMW-Newborn in two large Chicago birthing hospitals. Over 600 English- and Spanish-speaking participants were randomly assigned to receive the TMW-Newborn video or a control group educational video about Sudden Infant Death Syndrome (SIDS).

Results showed a significant increase in knowledge survey scores between pre- and post-intervention for participants in the TMW-Newborn treatment group. There was no significant increase in the control group's average scores. The increase for treatment participants remained significant 4 to 6 weeks after the intervention.

In addition to the Knowledge Survey, participants were asked a few questions concerning the UNHS and the video. We found that nearly 92% percent of all participants in the study stated that they understood what the UNHS hearing results meant for them and their infant after watching the video. Furthermore, in response to the questions about the video, 99% of participants found the information in the video helpful. 98% of them reported learning something new from the video and expressed willingness to recommend the video to a friend. 97% of all participants planned to try out strategies from the video at home and 87% of them agreed that it was convenient to view the video during the UNHS.

In summary, mothers of newborns who receive the TMW-Newborn educational intervention show increased knowledge and demonstrate an improved understanding of the critical importance of their newborn's early language environment for cognitive development and school readiness (Suskind et al., 2017).

### **Purpose**

The purpose of the proposed research is to perform testing of the Thirty Million Words Initiative Newborn Intervention (TMW-Newborn) with the primary goal of evaluating various implementation methods.

We hypothesize that the TMW-Newborn intervention will:

1. Significantly impact parent knowledge regarding the importance of UNHS follow-up
2. Significantly impact parent knowledge of child development

Additionally, we hypothesize that:

3. The 7-minute version of the video with questions interspersed will most significantly improve parent knowledge of child development
4. There will be no significant differences in effectiveness of the Spanish and English versions of the TMW-Newborn intervention

The hypotheses rely on the existing research data supporting the idea that parental understanding and beliefs will alter parental behavior, and consequently, that increased parental linguistic input will impact their child's cognitive development.

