### **Protocol**

We propose to perform a randomized implementation trial to evaluate the efficacy of various implementation methods of the TMW-Newborn educational intervention. The study will be

conducted in temporal proximity to the administration of the universal newborn hearing screen.

After routine delivery, postpartum mothers are admitted to the mother-baby unit for 48-72 hours. At Sacred Heart Hospital, study participation will be offered to every postpartum mother prior to discharge by a hearing screening technician, registered nurse, or registered hospital volunteer during the patient's hospital stay. Study participation will be offered to every mother whose child is receiving the hearing screening at the University of Chicago Medicine and Baptist Hospital-Pensacola. At the University of Chicago Medicine, study participation will be offered by a research assistant or hearing screening technician. At the Baptist Hospital-Pensacola, study participation will be offered by a nurse. The technician, nurse, or registered volunteer will give each mother an electronic tablet with the HIPAA Compliant TMW-Newborn Tech Platform that houses the TMW-Newborn intervention.

The patient experience through the TMW-Newborn intervention within the TMW Tech Platform is as follows:

- Participant selects language (English or Spanish) for viewing videos and completing surveys;
- Participant views Welcome and Consent Video, in which [name] (in English) or another health professional (in Spanish) introduce the study, explain participation, outline risks;
- Participants who agree to participate will then be randomized into one of four conditions:
  - Long TMW-Newborn intervention video without questions interspersed,
  - Long TMW-Newborn intervention video with questions interspersed,
  - Short TMW-Newborn intervention video without questions interspersed, or
  - Short TMW-Newborn intervention video with questions interspersed.
- Participant completes pre-intervention surveys: Baby SPEAK and non-identifying demographics items. These surveys take approximately 10 minutes to complete.
- Participant views TMW-Newborn intervention video, according to her randomized assignment outlined above.
- Participant completes post-intervention surveys: Baby SPEAK, UNHS, and fidelity of implementation.

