#### *Randomization*

The hearing screener, nurse, or volunteer will drop off tablets with participants, and only after the participants agree to participate by completing the tablet based consent will they be assigned to one of the four treatment conditions. The TMW-Newborn Web Platform will house the randomization tool that will randomize each participant into one of four treatment groups:

1. Long TMW-Newborn intervention video without questions interspersed,
2. Long TMW-Newborn intervention video with questions interspersed,
3. Short TMW-Newborn intervention video without questions interspersed, or
4. Short TMW-Newborn intervention video with questions interspersed.

There is equal likelihood of each randomization condition occurring.

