#### **Participants**

Participants will include a goal of 10,000 new mothers at Sacred Heart Hospital, University of Chicago Medical Center, and Baptist Hospital-Pensacola. 2,500 will be randomized into each of the four implementation conditions outlined above.

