#### **Analysis**

Paired t-tests will be used to analyze total survey scores before and after intervention. ANOVAs will be used to evaluate differences in outcomes based on SES and other variables in various experimental groups.

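### Hypothesis 2 claims an effect of the intervention, but with a video in every arm the paired before/after test can show only a pre/post change, which may include a retest or cueing gain

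*Combined protocol and SAP*

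**What the plan says.** The Purpose section lists as its second hypothesis that the intervention will "Significantly impact parent knowledge of child development". The Protocol Narrative uses the same causal language: "This one-time educational intervention will be impacting maternal awareness and knowledge".

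The Randomization section says the platform will "randomize each participant into one of four treatment groups". These are a long or a short TMW-Newborn video, each with or without interspersed questions. No group goes without the video, sees a different video, or takes only the post-video survey. The Participants section adds that "2,500 will be randomized into each of the four implementation conditions outlined above".

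The Protocol section sets the order on the tablet. Before the video: "Participant completes pre-intervention surveys: Baby SPEAK and non-identifying demographics items". After it: "Participant completes post-intervention surveys: Baby SPEAK, UNHS, and fidelity of implementation".

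The Analysis section has two sentences. The first is "Paired t-tests will be used to analyze total survey scores before and after intervention". The second assigns ANOVAs to differences by SES and other variables in the experimental groups. Neither sentence is tied to a numbered hypothesis.

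The Previous Research section describes two earlier randomised trials with over 600 participants in total, in which the control group saw a video about SIDS. Knowledge scores rose significantly with the TMW-Newborn video and the rise was still significant 4 to 6 weeks later. The control group's rise was not significant.

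**The concern.** An effect of the intervention is a contrast with what the same mothers would have scored without it. This trial observes no mother without a video. What it observes is each mother's score before and after, on the same instrument, in one sitting. Scores can rise on a second attempt because the items are familiar, or because the first attempt told the mother what to listen for. A paired test counts any such gain together with whatever the video taught.

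At stake is how hypothesis 2 will be reported. A significant paired result would naturally be written up as confirming the hypothesis, and the mean change could be quoted as what the video achieves. With a target of 10,000 mothers, statistical significance gives almost no protection against a small non-video component.

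**Working it through.** **1. Which test can serve hypothesis 2.** The ANOVAs compare groups of mothers who have all seen a video, so they cannot isolate the effect of seeing one. That leaves the paired t-test. It needs a score at both times; of the knowledge surveys listed, only Baby SPEAK appears both before and after the video, since the UNHS survey is given afterwards only.

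**2. What that test estimates.** Let v be the mean video effect and r the mean gain from retesting or cueing. If the two add (an assumption), then

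expected mean change = v + r.

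One observed quantity cannot identify two unknowns, and no arm has v = 0. If the pre-test instead changes how much the mother takes from the video, there is no single r to subtract, and the change still does not equal the effect of the video by itself.

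**3. Planned size.** 4 × 2,500 = 10,000, so the stated total is consistent. The documents give no alpha, power, effect size, SD or dropout, so the total cannot be reproduced as a power calculation. This point does not depend on it.

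**4. Smallest mean change that is significant.** In SDs of the change score, with two-sided alpha 0.05 (assumed) and the normal approximation, the threshold is 1.96/√n:

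- pooled, n = 10,000: 1.96/100 = 0.0196, about 0.020 SD
- one arm, n = 2,500: 1.96/50 = 0.0392, about 0.039 SD

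**5. What a retest gain alone could do.** The documents give no value for r, so a range is assumed. If the video had no effect at all, the probability of rejection would be Φ(r√n − 1.96) + Φ(−r√n − 1.96):

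| Assumed r (SD of change) | Pooled, n = 10,000 | One arm, n = 2,500 |
|---|---|---|
| 0 | 0.05 | 0.05 |
| 0.02 | 0.52 | 0.17 |
| 0.03 | 0.85 | 0.32 |
| 0.05 | 0.999 | 0.71 |

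The table shows how sensitive the test is. It does not predict that the video has no effect.

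**6. Overstatement if the video works.** Under additivity the excess is r. Relative to an assumed true effect it is r/v. For r = 0.05: 0.05/0.2 = 25%, 0.05/0.5 = 10%, 0.05/0.8 = 6%. For r = 0.02: 10%, 4% and 2.5%. With r = 0 there is no excess.

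**7. Whether the earlier control group rules out r.** The protocol gives no estimate or interval for it. If the 600 or so mothers were split equally and the two trials pooled (assumed), there were about 300 controls, and the half-width of a 95% interval for their mean change is 1.96/√300 = 0.113 SD. A true control gain of 0.05 SD would have been significant only 14% of the time, and one of 0.10 SD only 41%. A non-significant result therefore does not exclude gains of the size considered here. The protocol also calls that instrument only a knowledge survey and does not say that it was Baby SPEAK.

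**8. Format comparisons.** For arms j and k with a common r, the difference in mean change is (v_j + r) − (v_k + r) = v_j − v_k, so r cancels.

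**The case against.** The strongest reply is that this trial was not built to establish efficacy. Its stated primary goal is to compare implementation methods; the controlled efficacy question went to the two earlier trials, and leaving out a control here follows from that sequence. Hypothesis 2 asserts that an impact exists and gives no size, so if the video works, as the earlier results suggest, a significant paired test points to the right answer. The plan promises no effect estimate or confidence interval that could mislead. Nothing in the documents shows a positive retest gain, and if the video effect is large, a small gain hardly matters.

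Much of this stands. The earlier trials make a real video effect plausible, the hypothesis is not the primary one, and the size of any bias is unknown. The reply does not remove the mismatch: the causal wording remains, and the only test available for it would give the same significant result for a sufficiently large retest gain as for a video effect. The earlier trials are outside evidence, and it is not stated that they used the same instrument.

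A reader might infer that this trial can say nothing causal about the video. The documents do not support that. Allocation to format is randomised, so a difference between formats would itself be causal evidence that video format affects knowledge. A reader might also infer that hypothesis 2 is probably false or that its test will give the wrong answer. The documents do not support that either.

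**Conclusion.** The point holds as a limit on what hypothesis 2 can conclude. On this trial's before/after data, the paired test supports a statement about pre/post change. It does not support a statement about the size of the video's effect.

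The size of the problem cannot be fixed from the documents. A retest gain of zero is compatible with them and would mean no bias. If there is a gain and it adds to the video effect, the overstatement equals that gain. The firm figures are the significance thresholds of about 0.020 SD pooled and 0.039 SD per arm, which assume two-sided alpha 0.05 and complete pairs at the planned numbers. They show that a very small non-video gain could be significant. The retest gains, video effects and earlier control-group size used in the working are illustrations.

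It would be wrong to extend the point to the primary goal or to hypothesis 3. A shift common to all arms does not bias the randomised format comparisons.

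**What to change.** In the Purpose section, restate hypothesis 2:

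> Mean Baby SPEAK total score will be higher after the video than before it.

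In the Analysis section, add:

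> For hypothesis 2, the mean within-mother change in Baby SPEAK total score will be reported with its 95% CI and the number of mothers with both surveys, pooled and per arm, as a pre/post change that may include a retest or cueing gain; it will not be reported as the size of the video effect. Causal conclusions from this trial will rest on the randomised comparisons between formats. The earlier controlled trials will be cited as external support, stating whether they used the same instrument.

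This needs no new arm, data or platform change, and no change to the sample size. The cost is a more modest conclusion for a non-primary hypothesis.

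### Hypothesis 4 rests on a non-significant Spanish–English test, which could reflect only a small number of Spanish users; the plan gives no other criterion for similar effectiveness.

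*Combined protocol and SAP*

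**What the plan says.** The Purpose section describes the trial as one "with the primary goal of evaluating various implementation methods". It lists four hypotheses, the last two introduced as additional. The fourth is: "There will be no significant differences in effectiveness of the Spanish and English versions of the TMW-Newborn intervention".

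The Protocol section shows how language enters the data. Before consent and randomisation, "Participant selects language (English or Spanish) for viewing videos and completing surveys". Baby SPEAK is then given before the video ("Participant completes pre-intervention surveys: Baby SPEAK and non-identifying demographics items") and again after it ("Participant completes post-intervention surveys: Baby SPEAK, UNHS, and fidelity of implementation"). It is the only survey listed at both times.

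The Participants section sets a goal of 10,000 mothers, of whom "2,500 will be randomized into each of the four implementation conditions outlined above"; it gives no number by language. The Analysis section has two sentences. One plans paired t-tests of total scores before and after the video. The other says "ANOVAs will be used to evaluate differences in outcomes based on SES and other variables in various experimental groups". Neither mentions hypothesis 4, a margin, a confidence interval or a significance level.

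**The concern.** A test that fails to reject is not evidence that two versions work equally well. It may mean that the difference is small, or that the estimate is too imprecise to tell. As hypothesis 4 is worded, both outcomes look like success, and for any real difference the chance of that success rises as fewer mothers choose Spanish. The criterion also fails in the other direction: with many Spanish users, a trivial difference would count against the hypothesis.

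The contrast also lies outside the randomisation. Mothers select their own language, and the same selection fixes both the video and the survey version. A difference in scores therefore mixes differences between the mothers, between the videos and between the two language versions of the survey. The plan does not describe the comparison as observational. At stake is a statement that the Spanish version works as well as the English one, resting on a result that might show only a lack of information.

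**Working it through.** **The plan's own figure.** 4 × 2,500 = 10,000, which matches the enrolment goal. No alpha, power, SD, effect size or margin is given, so nothing further can be reproduced.

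**Inputs.** From the documents: total N = 10,000. Assumed, because the documents do not give them: number of Spanish users nS, complete data, a two-sided 5% test, and a true gap of 0.2 SD in the score compared, with equal SD in both groups.

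**Formulas.**
- SE = sqrt(1/nS + 1/(10,000 − nS)), in SD units.
- Chance of non-significance = 1 − [Φ(0.2/SE − 1.96) + Φ(−0.2/SE − 1.96)].
- Chance that a 90% interval lies inside ±0.2 SD when the true difference is zero = max(0, 2Φ(0.2/SE − 1.645) − 1).

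For nS = 100: SE = sqrt(0.01 + 0.000101) = 0.1005; 0.2/0.1005 = 1.99; Φ(0.03) = 0.512; chance of non-significance = 0.488.

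| Spanish users | SE | 95% CI half-width | 0.2 SD gap non-significant | Similarity shown (margin 0.2 SD, 90% CI, true gap 0) |
|---|---|---|---|---|
| 100 | 0.1005 | 0.197 | 49% | 27% |
| 200 | 0.0714 | 0.140 | 20% | 75% |
| 500 | 0.0459 | 0.090 | 0.8% | 99% |
| 1,000 | 0.0333 | 0.065 | about 0% | about 100% |

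**Relation to change scores.** If pre and post scores have equal SD and correlation r, the SD of change is sqrt(2(1 − r)) times the single-score SD. At r = 0.5 this is sqrt(1) = 1, so the table then applies to change directly.

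**Range under adjustment.** With baseline adjustment, SE is multiplied by sqrt((1 − r²)V), where V is the variance inflation from correlation between language and the covariates. Between a favourable case (r = 0.7, V = 1) and an unfavourable one (r = 0.5, V = 2), the chance of missing a 0.2 SD gap runs from 20% to 63% with 100 Spanish users, 2.5% to 37% with 200, and under 0.1% to 5.5% with 500.

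**Two reference points.** If the true difference is zero, the test is non-significant 95% of the time at any enrolment. With 2,000 Spanish users, SE = sqrt(0.0005 + 0.000125) = 0.025, so a true gap of 0.1 SD is 4 SEs and is significant with probability Φ(4 − 1.96) = 0.98.

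**What an interval rule changes.** If the true gap equals a 0.2 SD margin, a 90% interval falls wholly inside the margin at most 5% of the time whatever nS is, leaving confounding aside.

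**Confounding.** The adjusted and change-score estimates differ by (1 − slope) × baseline gap. For an assumed baseline gap of 0.3 SD this is 0.3 × 0.5 = 0.15 SD at slope 0.5 and 0.3 × 0.3 = 0.09 SD at slope 0.7. Neither estimate is clearly right for self-selected groups, so both should be shown.

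**The case against.** The best defence is that hypothesis 4 is an additional hypothesis, the main aim is to compare implementation methods, and the trial is large. If 500 or more mothers use Spanish, a 0.2 SD gap would seldom be missed, and with 2,000 the hypothesis as worded would be a demanding test. All of this stands and limits the point to a small Spanish group. It does not rescue the criterion, because the documents do not say how many Spanish users to expect. The Previous Research section does not help: "Over 600 English- and Spanish-speaking participants were randomly assigned to receive the TMW-Newborn video" or a control video, with no split by language.

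A reader might infer several stronger things that the documents do not support:
- *That language will not be analysed.* Language is selected on the platform, and the unnamed other variables in the ANOVA sentence could well include it. What is missing is a sound criterion.
- *That the plan will report non-significance as proof of equivalence.* It states no reporting rule either way.
- *That the trial is too small.* That depends on the Spanish number, whose absence is missing detail and not an error in itself.
- *That the comparison of the four video conditions is compromised.* Those are randomised and unaffected.

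It is also fair to say that a formal equivalence test gains little on a confounded secondary contrast. For that reason the remedy should allow an estimate and interval with no equivalence claim.

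**Conclusion.** The point holds as a fault in the criterion for one additional hypothesis. Absence of significance is the only standard attached to it, and that standard can be met through imprecision alone. In the unadjusted illustration, the chance of missing a 0.2 SD gap falls from about one in two at 100 Spanish users to one in five at 200 and under 1% from 500 upwards. These figures rest on assumed Spanish numbers, an assumed meaningful gap, complete data and a 5% two-sided test. The confounding by self-selected language, and the shared language of video and survey, remain at any sample size. The change should be made, but it does not bear on the trial's main comparison.

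**What to change.** Before the data are seen, replace the non-significance criterion with the following:

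1. Report the Spanish–English difference in Baby SPEAK pre-to-post change with its confidence interval at a stated level. This keeps the plan's own pre-post measure. Report the baseline-adjusted estimate as well.
2. State that a non-significant result will not be read as similar effectiveness. Claim similarity only if the interval for the change difference lies inside a margin fixed and justified in advance. If no margin can be justified, report the estimate and interval without an equivalence claim.
3. Label the comparison observational, and say that it cannot isolate the video version because mothers choose their language and video and survey language coincide.

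The data are already in the platform flow: language choice and Baby SPEAK at both times. The work lies in agreeing a margin, which needs scale information that the documents do not give; the earlier trials might supply it if their survey is comparable. The main downside is that with few Spanish users the answer may be inconclusive. Under the working assumptions above, similarity at a 0.2 SD margin would be shown only 27% of the time with 100 Spanish users even if the versions were identical in effect.
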